7.0 DRUG FORMULATION AND PROCUREMENT

7.1 Caphosol

7.1.1 Other Names

Supersaturated calcium phosphate rinse

7.1.2 Classification

Topical oral agent

7.1.3 Mode of Action

Caphosol is a supersaturated aqueous solution of calcium phosphate and high concentrations of calcium and phosphate ions are hypothesized to diffuse into epithelial intracellular spaces and permeate mucosal lesions in oral mucositis. Caphosol resembles human saliva and is designed to restore the normal ionic and pH balance in the oral cavity. In addition, calcium may modulate the inflammatory response and tissue repair processes and phosphate may be involved in repairing damage to the mucosal surface. There are no known interactions between Caphosol and other drugs. No systemic toxicities have been described when using Caphosol as a mouth rinse.

7.1.4 Storage and Stability

Although commercially available, Caphosol will be considered an investigational product for purposes of this clinical trial. Investigational products are required to be stored in the Investigational Drug service area by central pharmacy in the lower level of the West Tower.

Caphosol is supplied as two separately packaged aqueous solutions; a 15 mL phosphate solution and a 15 mL calcium solution. When mixed, Caphosol solution contains dibasic sodium phosphate 0.032%, monobasic sodium phosphate 0.009%, calcium chloride 0.052% and sodium chloride 0.569% in purified water. Caphosol is stored at room temperature conditions for the duration of its shelf life. It should not be refrigerated.

7.1.5 Dose Specifics

For the purposes of this study, Caphosol will be administered topically at the dose of 30 mL QID. Dose frequency may be increased up to 6 times daily for symptoms of oral mucositis.

If younger patients (age ≤ 6 years) are unable to tolerate the full volume, the volume may be reduced to a total of 10-20 mL per dose (5-10 mL x 2), as tolerated. For patients unable to successfully swish and spit, caregivers may paint

the Caphosol solution using medical sponge swabs on the oral mucosa x 2 for each dose.

7.1.6 Administration

Investigational Pharmacy will dispense the agent for this clinical trial and place the unit of use, (oral syringe A & B) in a baggie with label for each dose. Unit dosing the oral syringe A&B in a baggie with med label and date/time due should ensure both A&B being administered.

This process means that the product will be in the patient's med drawer with other meds. If the dosing schedule is 6 doses per day (not 4), then Investigational pharmacy would send the evening and overnight doses with regular meds and bring the AM doses up each morning. Patients who receive Caphosol in the outpatient setting will receive a home supply for 2 weeks with appropriate drug labeling and instructions for use and will be evaluated in clinic for compliance and proper administration of the agent.

Caphosol will be supplied in two 15 mL syringes per dose. These are to be mixed together within 15 minutes of dose administration. Patients are to swish and gargle (if able) one half of the mixture (approximately 15 mL) for one minute, and then spit. Immediately repeat with second half of mixture.

For patients unable to successfully rinse and spit, caregivers may paint their mouth (using medical sponge swabs) with the solution x 2. Prior to swabbing the patient's mouth, mix half of the 2, 15 mL syringes into a cup and dip swab prior to coating the inside of the patient's mouth. Repeat

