1.0 BACKGROUND

Mucositis in Children, Adolescents and Young Adults Undergoing Chemotherapy

Oral mucositis, a common and debilitating complication of cancer therapy, is an inflammatory injury to the epithelial and sub-epithelial cells of the oral mucosa. Oral mucositis is thought to develop according to a five-stage model: 1) initiation; 2) up-regulation with generation of messengers; 3) signaling and amplification 4) ulceration with inflammation; and 5) healing, and typically develops 7-14 days into a chemotherapy course (1).

The incidence and severity of oral mucositis depends on many factors including the age and diagnosis of the patient, the specific treatment regimen, underlying oral hygiene and genetic factors (2-4). The incidence of oral mucositis in patients receiving chemotherapy ranges from around 40% of patients receiving myelosuppressive chemotherapy for solid tumors to 70-90% of patients receiving myeloablative therapy prior to stem cell transplant (1, 5, 6). A commonly used grading scale for mucositis is the Common Terminology Criteria for Adverse Events (CTCAE version 4.0) grading scale, where grading is based on both subjective and objective assessments on a 5 point scale (Grade 1 to Grade 5).

Adverse Event	1	2	3	4	5
Mucositis Oral Definition: A disorder characterized by inflammation of the oral mucosal.	Asymptomatic or mild symptoms; intervention not indicated	Moderate pain; not interfering with oral intake; modified diet indicated	Severe pain; interfering with oral intake	Life-threatening consequences; urgent intervention indicated	Death

From the Common Terminology Criteria for Adverse Events (CTCAE) Version 4.0 Published: May 28, 2009 (v4.03: June 14, 2010) U.S. DEPARTMENT OF HEALTH AND HUMAN SERVICES National Institutes of Health National Cancer Institute, p. 19

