2.0 STUDY OVERVIEW

Eligible patients will be identified in the oncology clinic and/or the oncology ward and consented/enrolled on study. Study patients randomized to the Caphosol arm will begin Caphosol therapy prior to administration of systemic chemotherapy on Day 1 according to protocol. Caphosol administration will continue through the planned chemotherapy administration and until stopping criteria are met. Chemotherapy will be administered either in the MACC Fund Center or the inpatient service. Once the chemotherapy is complete the patient will be discharged to home and followed in the MACC Fund Center at regular intervals as dictated by standards of care. Caphosol treatment will continue at home as outlined in the protocol for 7 days following completion of chemotherapy and adequate neutrophil recovery, or until oral mucositis symptoms resolve, whichever occurs later. In the event the patient requires hospital admission, Caphosol treatment will continue according to protocol. The patient/family will keep a daily drug diary of administration of Caphosol throughout each cycle which will be reviewed by the study team at

each study visit. As well patients in each cohort will record in their diary other oral topical agents they are using and any narcotic and non-narcotic medications used for treatment of pain/mucositis.

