5.0 TREATMENT PLAN

This study is a randomized, controlled trial evaluating the use of topical Caphosol therapy to prevent oral mucositis (Grade ≥ 2) in children, adolescents and young adults undergoing chemotherapy. At the time of enrollment, patients will be randomized to either the control arm or the Caphosol arm. The treatment period will extend from the start of chemotherapy and continue for 7 days after completion of chemotherapy AND until the ANC is > 500 after nadir (count recovery) or until the symptoms of oral mucositis resolve; whichever occurs last.

Treatment

Caphosol Arm: Subjects randomized to the **Caphosol Arm** will use Caphosol 4 times per day as follows:

- Each dose consists of two 15 mL syringes, to be mixed at time of administration. Caphosol must be used within 15 minutes of mixing.
 - Subjects may increase the use to 6 times per day if they have symptoms of mucositis.
- Using one of the syringes, rinse and gargle (if patient is able) for one minute and then spit. Repeat using the remaining syringe.
 - For younger patients (less than or equal to 6 years of age), volume may be reduced to two syringes containing 5-10 mL each.
 - For patients unable to successfully rinse and spit, caregivers may paint their mouth (using medical sponge swabs) with the solution two times. Prior to swabbing the patient's mouth, squirt one of the syringes into a cup and using the medical sponge, soak up the solution and use the swab to coat the inside of the patient's mouth. Repeat using the second syringe.
- Patients are to avoid other oral medications, other mouth cares and food or drink for 15 minutes after using Caphosol.

- Patients will also use Biotene (5-10 mL) to swish and spit after the 15 minutes has passed. Biotene is part of our standard of care to prevent oral infections in oncology patients.

Control Arm: Subjects randomized to the **Control Arm** will use Biotene only 4 times per day as follows:

- Use 5 to 10 mL of Biotene to swish and spit
 - For patients unable to successfully rinse and spit, caregivers may paint their mouth (using medical sponge swabs) with the solution two times. Prior to swabbing the patient's mouth, pour Biotene into a cup and using the medical sponge, soak up the solution and use the swab to coat the inside of the patient's mouth. Repeat with a second swab.

The following will be observed:

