- Incidence of oral mucositis. Oral mucositis will be defined and characterized by the Common Terminology Criteria for Adverse Events (CTCAE) Version 4.0 as Grade 1-4.
- Severity of oral mucositis, according to:
 - Age-appropriate pain scales (LIKERT and FACES)
 - CTCAE V 4.0 grading
 - Total narcotic usage (both the total amounts in milligrams and the number of days the patient required intravenous narcotic therapy as well as any increase of dose above baseline for patients who are on scheduled chronic use of narcotics)
 - Number of hospital days with oral mucositis present
 - TPN use and duration

The following will be observed on all patients on the Caphosol arm, via the study diary:

- Missed doses of Caphosol and reason
- Side effects attributed to Caphosol therapy
- Use of any other oral topical agents for oral mucositis (dose, schedule, number of doses taken) such as biotene/ chlorhexidine rinses and/or magic mouthwash.
- Use of any non-narcotic pain medications for oral mucositis (dose, schedule, number of doses taken)
- Use of any narcotics for oral mucositis (dose, schedule, number of doses taken)

The following will be observed on all patients on the Biotene arm, via the study diary:

- Use of any other oral topical agents for oral mucositis (dose, schedule, number of doses taken) such as chlorhexidine rinses and/or magic mouthwash.
- Use of any non-narcotic pain medications for oral mucositis (dose, schedule, number of doses taken)
- Use of any narcotics for oral mucositis (dose, schedule, number of doses taken)

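### Compliance checks, diary review and missed-dose recording are specified for Caphosol only, with nothing matching for the controls' assigned Biotene, so unequal attention could favour Caphosol

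*Combined protocol and SAP*

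**What the plan says.** For Caphosol, the combined protocol and SAP sets out three forms of attention to how the rinse is used.

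- **Clinic check.** Under section 7.1.6, patients who take Caphosol as outpatients get a two-week home supply with labelling and instructions, and "will be evaluated in clinic for compliance and proper administration of the agent". No frequency is given.
- **Diary review.** Section 2.0 makes this a task for every visit: "The patient/family will keep a daily drug diary of administration of Caphosol throughout each cycle which will be reviewed by the study team".
- **Missed doses.** The Caphosol-arm diary list in section 5.0 includes "Missed doses of Caphosol and reason". The same list asks for other topical agents, "such as biotene/ chlorhexidine rinses and/or magic mouthwash", so Biotene use in this arm is to be recorded.

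For controls, section 5.0 assigns Biotene four times a day, with a volume and a swab technique for those who cannot rinse. Table 1 and Table 2 keep controls on the study diary. Section 2.0 says that "patients in each cohort will record in their diary other oral topical agents they are using", along with pain medicines. The control diary list in section 5.0 covers other topical agents (its examples omit Biotene), non-narcotic pain medicines and narcotics. It has no item for Biotene doses taken or missed. Table 2 schedules evaluations at least weekly and lists no compliance or technique check for either arm.

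**The concern.** Both arms are assigned a rinse regimen, and the Caphosol arm uses Biotene as well. If one arm is regularly asked whether and how it rinses, its mouth care as a whole may improve, Biotene included. Section 1.0 lists among the factors behind incidence and severity "the specific treatment regimen, underlying oral hygiene and genetic factors", which gives a plausible route from mouth care to the primary endpoint. No masking or placebo rinse is described, so nothing in the design evens out the attention.

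At stake is the first primary objective, whether Caphosol itself prevents Grade 2 or higher mucositis. Any benefit of attention would be counted as a benefit of Caphosol. Analysis could not undo this. Section 4.3 allows covariate adjustment if imbalance exists after randomisation, but the controls' Biotene use is not a listed data item, so the report could not even show that background care was similar.

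**Working it through.** **1. The arms side by side**

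| Item | Caphosol arm | Control arm |
|---|---|---|
| Assigned rinse (5.0) | Caphosol four times daily, plus Biotene | Biotene four times daily |
| Clinic check of compliance and administration (7.1.6) | Yes, outpatients | None stated |
| Administration diary reviewed by study team (2.0) | Yes, for Caphosol | None stated for Biotene |
| Missed doses with reason (5.0) | Yes, for Caphosol | Not listed |
| Biotene use in diary (5.0) | Listed as another topical agent | Not listed |
| Diary kept (Tables 1 and 2) | Yes | Yes |
| Seen at least weekly (Table 2) | Yes | Yes |

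The diary form itself is not in the document, so this rests on the items the text lists.

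**2. The plan's own figure**

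Section 10.3 gives 48 per group for a 30% difference, alpha 0.05 and power 80%. Taking 55% against 25%, two-sided:

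n = [1.96·√(2·0.40·0.60) + 0.8416·√(0.55·0.45 + 0.25·0.75)]² / 0.30² = (1.358 + 0.555)² / 0.09 = 40.7

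With continuity correction: (40.7/4)·[1 + √(1 + 4/(40.7·0.30))]² = 47.1, rounded up to 48.

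So 48 per arm reproduces as a 30-point absolute difference. The present point does not depend on it; only the 48 is carried forward.

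**3. What a pure attention effect would do**

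Assumptions, none of them from the documents: Caphosol has no effect, and closer supervision alone lowers the Grade 2 or higher rate by d points in the Caphosol arm. The test is two-sided at 0.05 with 48 per arm. Section 10.3 does not state sidedness. The control rate is 50% (top of the range in section 10.3), or 40% (the solid-tumour figure in section 1.0) as a check.

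The normal approximation for a significant result favouring Caphosol is Φ[(d − 1.96·s₀)/s₁], where s₀ = √(2·p̄·(1−p̄)/48) and s₁ = √([p₁(1−p₁) + p₂(1−p₂)]/48).

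For 50% against 40%: s₀ = √(2·0.45·0.55/48) = 0.1016 and s₁ = √((0.25 + 0.24)/48) = 0.1010. Then (0.10 − 0.1990)/0.1010 = −0.98, and Φ = 16.3%.

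The table sums the two binomial distributions over all outcomes, counting only results that favour Caphosol. Section 10.2 names logistic analysis, or Fisher's exact test if numbers are small. The uncorrected chi-square stands in for the former.

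| d | Control 50%: Fisher | Control 50%: chi-square | Control 40%: Fisher | Control 40%: chi-square |
|---|---|---|---|---|
| 0 | 1.6% | 2.6% | 1.5% | 2.5% |
| 5 points | 4.8% | 7.3% | 4.6% | 7.2% |
| 10 points | 12.0% | 16.7% | 12.2% | 17.6% |
| 15 points | 24.7% | 31.9% | 26.9% | 35.4% |

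Counting significant results in either direction, chi-square at a 50% control rate gives 8.0%, 16.8% and 32.0% for the three shifts. The one-direction figures are the relevant ones, because the suspected bias runs one way.

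**The case against.** A good deal can be said on the other side.

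- **The placement is natural.** The clinic check sits in the section on the investigational product. Biotene is background care ("Biotene is part of our standard of care to prevent oral infections in oncology patients") and has no product section. Checking use of a study product is ordinary conduct. This stands, and it explains the asymmetry, but it does not remove it: section 5.0 also makes Biotene the control regimen, with a frequency and a technique.
- **Controls are not left alone.** They keep a diary and are seen at least weekly, and inpatients in both arms are assessed daily. A reader might infer that controls' rinsing is never checked, and that the trial compares supervised with unsupervised mouth care. The documents do not support that. They show only that no check is provided for; staff may well ask.
- **The check is of Caphosol, and in outpatients.** It concerns the agent, a two-syringe product that must be mixed. Spill-over to general mouth care is an inference. The per-dose labelled bags in section 7.1.6 read as inpatient dispensing, so they should not be counted as extra outpatient support.
- **The route to the endpoint is indirect.** Section 1.0 speaks of underlying oral hygiene, alongside patient characteristics. Section 5.0 says Biotene is used against oral infections. No section says that better Biotene adherence lowers mucositis.
- **The shifts have no source.** Ten to 15 points is a third to a half of the 30-point effect the trial is sized for. With Fisher's test, a 5-point shift leaves the chance below 5%.

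These points limit how strongly the matter can be put. They do not supply a matching check or record for controls.

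**Conclusion.** The point holds as an avoidable one-arm difference in attention. As written, the plan checks, reviews and records Caphosol use and provides nothing equivalent for the Biotene assigned to controls. The likely direction favours Caphosol.

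Its size is unknown. The calculation shows only what would follow from assumed shifts. At a 50% control rate, 5 points would roughly triple the chance of a false result favouring Caphosol (1.6% to 4.8% with Fisher's test, 2.6% to 7.3% with chi-square), and 10 or 15 points would raise it to 12-17% or 25-32%. If Caphosol does work and the two effects add, its benefit would be overstated by the attention effect.

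This rests on three assumptions: that the listed diary items are complete, that attention to Caphosol carries over to general mouth care, and that mouth care affects Grade 2 or higher mucositis. The last two are plausible but not stated. It would go too far to say that a positive result would be due to supervision. The change is nevertheless worth making before enrolment is far advanced, because unrecorded control Biotene use cannot be recovered later.

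**What to change.** Amend sections 2.0, 5.0 and 7.1.6 and Table 2 as follows.

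1. List Biotene doses taken and missed as diary items in both arms.
2. Have the study team review both arms' diaries at each study visit.
3. At existing visits, apply one brief scripted check of compliance and technique to the assigned rinse regimen: Biotene in controls, Caphosol and Biotene in the Caphosol arm.
4. State in section 10.2 that adherence will be reported by arm.

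No dose, schedule or sample size changes. The cost is a few minutes per visit for study nurses who already see both arms at least weekly, plus a small revision of the diary. One downside is that control mouth care may become slightly better than in routine practice. Equal checks would not cure the lack of masking, which remains a separate limitation.

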7.1.7 Side Effects

No side effects are expected. Previous studies have shown Caphosol to be safe and well-tolerated with no known side effects, even when inadvertently swallowed.

Pregnancy: It is not known if Caphosol is teratogenic or passes through breast milk; therefore, pregnant and lactating patients will not be eligible for enrollment on study. Patients who become pregnant while on study receiving Caphosol will become ineligible and removed from protocol therapy.

8.0 ADVERSE EVENT MONITORING, DOCUMENTATION AND REPORTING

Toxicity and adverse events will be classified according to NCI's Common Terminology Criteria for Adverse Events V 4.0 (CTCAE) and reported on the schedule below. A copy of the CTCAE can be downloaded from the CTEP home page: http://ctep.cancer.gov/protocolDevelopment/electronic_applications/ctc.htm#ctc_40

8.1 Definitions

The following definitions are based on the Code of Federal Regulations Title 21 Part 312.32 (21 CFR 312.32(a)).

Adverse Event: Any untoward medical occurrence associated with the use of a drug in humans, whether or not considered drug related.

Suspected Adverse Reaction: Any adverse event for which there is a reasonable possibility that the drug caused the adverse event.

Life-Threatening Adverse Event Or Life-Threatening Suspected Adverse Reaction: An adverse event or suspected adverse reaction is considered “life-threatening” if, in the view of either the investigator or sponsor, its occurrence places the patient or subject at immediate risk of death.

Event Attribution Categories: CTCAE does not define an AE as necessarily ‘caused by a therapeutic intervention.’ The clinical investigator must assign attribution for an adverse event after naming and grading of the event.

Attribution	Description
Unrelated	The AE is clearly NOT related to the intervention
Unlikely	The AE is doubtfully related to the intervention
Possible	The AE may be related to the intervention
Probable	The AE is likely related to the intervention
Definite	The AE is clearly related to the intervention

Unanticipated (unexpected) adverse event or unexpected suspected adverse reaction as defined by the Children’s Hospital Wisconsin (CHW) IRB are those that are *not* already described as potential risks in the consent form, *not* listed in the Investigator’s Brochure or *not* part of an underlying disease.

Expedited (Rapid) Reporting: Certain events may require rapid notification to entities providing patient safety oversight (e.g. IRB) as detailed in Section 8.3.

	Grade 1	Grade 2		Grade 3		Grade 4 and 5
	Expected or Unexpected	Expected	Unexpected	Expected	Unexpected	Expected or Unexpected
Unrelated Unlikely	Not required	Not required	Not required	Not Required	Required	Required
Possible Probable Definite	Not required	Not required	Not Required	Not Required	Required (Non hematologic only)	Required

8.2 Adverse Event Documentation

Adverse events occurring after the initiation of any study treatment must be documented. There are no expected toxicities from the addition of Caphosol therapy.

Adverse event documentation requirements will be determined based on grade, expectedness and relationship to study therapy as follows:

Stopping Rule Events: The following events count toward a study stopping rule per Section 10.3 and must be reported to the MCW Study Coordinator.

- Any Grade 4 non-hematologic treatment related event
- Any death, regardless of cause during the reporting period for this study from initiation of study treatment to end of study.

Events that count toward an early stopping rule do not necessarily constitute a serious adverse event requiring expedited reporting and should be reported as such only if they meet the criteria for expedited reporting to the IRB as defined in section 8.3.

All patients will be monitored through the treatment period, as it is expected that most treatment related adverse events will occur during this period.

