5.1 Treatment Plan Schema

[figure not shown]

Table 1: Treatment Plan

Day	Agent/Procedure
Enrollment	Randomization to control arm or Caphosol arm
Day 1 of Chemotherapy	Start study diary IF on Caphosol Arm : Start Caphosol, 30 mL QID
Completion of Chemotherapy	Control Arm : Continue study diary and Biotene for 7 days after therapy completed AND until ANC > 500 after nadir or until mucositis resolution, whichever occurs later. Caphosol Arm : Continue Caphosol, Biotene, and study diary for 7 days after therapy completed AND until ANC > 500 after nadir or until resolution of oral mucositis; whichever occurs latest.

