8.3 Adverse Event Reporting Requirements

The reporting period for this study is from initiation of study treatment through completion of Caphosol therapy; however after this time point, the investigator must report upon knowledge any study treatment related event meeting the expedited reporting criteria in the following table.

Regulatory Reports To	Criteria for Reporting	Timeframe	Form to Use	Copy AE To:
CHW IRB	UPIRSO: Any event which is unanticipated, involved new or increased risk to subjects, and was at least possibly related to study procedures through Day 60 or the start of a new treatment whichever is earlier	5 calendar days	SAE	MCW SAE Coordinator
	Other problems or events meeting the definition of UPIRSO			
MCW DSMC	Any event that counts toward a study stopping rule.	Within 24 hours of PI notification	SAE	MCW SAE Coordinator
	All unexpected grade 3, and all grade 4, and 5 adverse events, as well as any others requiring expedited reporting as defined in this protocol.	Grades 4 & 5 events must be reported to the DSMC within 5 calendar days of study staff's knowledge	SAE	MCW SAE Coordinator

If the SAE meets CHW IRB criteria for expedited reporting, then an official signed report is submitted to the IRB within 5 days. Adverse events which did not meet the CHW Prompt Reporting Criteria as outlined in the CHW IRB policy and procedure should be reported to the IRB at time of continuing review. All deaths, regardless of the cause, need to be reported to the PI within 48 hours and then reported to the IRB.

The Study Coordinator will provide the MCW's Data and Safety Monitoring Committee (DSMC) and CHW IRB with the SAE in an appropriate format depending on the individual SAE (as reported or in a summary format).

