10.0 STATISTICAL CONSIDERATIONS

10.1 Statistic Endpoints

The study will not stratify based on diagnosis. The effectiveness of the study will be based on comparing incidence and severity of oral mucositis. Safety and tolerance will be based on the differential incidence of severe adverse events. A continuous sequential boundary will be used to terminate the study if the difference in adverse events occurs at a rate of 10% or greater at the interim analysis performed at the end of study month 3. A continuous sequential boundary will also be constructed for a differential rate of 5%.

An interim analysis will be conducted half way through using the O'Brien-Fleming rule for early stopping because of success.

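### Unresolved mucositis can lengthen adverse event observation, so if Caphosol works the between-arm comparison of severe adverse events is tilted modestly in its favour

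*Combined protocol and SAP*

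**What the plan says.** - **Monitoring.** Section 8.2: "All patients will be monitored through the treatment period".
- **End of that period.** Section 5.0 requires 7 days after chemotherapy and continues "until the ANC is > 500 after nadir (count recovery) or until the symptoms of oral mucositis resolve; whichever occurs last". The Section 5.1 table applies the same rule to controls: "7 days after therapy completed AND until ANC > 500 after nadir or until mucositis resolution, whichever occurs later". I read this as the latest of three conditions.
- **Reporting period.** Section 8.3 runs it "from initiation of study treatment through completion of Caphosol therapy". Afterwards, "the investigator must report upon knowledge any study treatment related event meeting the expedited reporting criteria".
- **Data collection.** Under Section 5.5 it runs through planned therapy, or stops when the patient meets the criteria for removal from protocol therapy or for going off study. Section 5.6.1 lists adverse events and intolerance among the removal criteria.
- **Comparison.** Section 10.1: "Safety and tolerance will be based on the differential incidence of severe adverse events". It names a 10% difference as the stopping trigger and plans a second boundary at 5%. It gives no common observation interval and no adjustment for time at risk.

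**The concern.** One of the three conditions that close the safety window is the efficacy outcome. A patient without mucositis leaves at the floor (7 days after chemotherapy, with counts recovered). A patient whose mucositis outlasts the floor stays under observation until it clears. All patients are receiving chemotherapy, so severe events can occur in the added days. The Section 8.1 table requires reporting of unrelated Grade 4-5 and unexpected Grade 3 events, so background events can enter the comparison.

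If Caphosol prevents mucositis, fewer of its patients have an extended window, and its incidence of severe events is lower for that reason alone. More patients would not remove this bias.

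Two further features affect the arms unequally. Completion of Caphosol therapy has no meaning for a control patient, so the Section 8.3 period is undefined in that arm. And because Section 5.5 lets data collection stop at removal from protocol therapy, intolerance of Caphosol can itself shorten observation in the Caphosol arm.

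**Working it through.** **1. The plan's own figure.** Section 10.3 gives 48 per group for a 30% difference, alpha 0.05, power 80%. Use n = [z(0.975)·√(2p̄(1−p̄)) + z(0.80)·√(p1(1−p1) + p2(1−p2))]² / (p1−p2)², two-sided (an assumption, since sidedness is not stated). For 25% v 55% this gives 41 per arm, or 48 with continuity correction, which matches. For 50% v 20% it gives 39, or 45 corrected. The effect is therefore 30 absolute points. Below I use mucositis in 50% of controls (top of the stated range) and 20% on Caphosol.

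**2. Inputs for the window.**
- From Section 1.0: onset at day 7-14 of a course; mean mucositis duration 7.22 days (control) and 3.72 days (Caphosol), both from an adult transplant trial.
- Assumed: chemotherapy ends on day 5, so the earliest close is 5 + 7 = day 12; ANC recovery has mean day 14 to 25, SD 3; severe-event risk is 10% to 50% over the mean time to ANC recovery, at a constant daily hazard; one course; no true safety difference.

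**3. Single-course simulation** (400,000 patients per arm). Window = max(day 12, ANC recovery, mucositis end), with uniform onset and gamma durations. The last three columns are Caphosol minus control, in points, at each severe-event risk.

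| Mean ANC recovery day | Control mucositis cases outlasting the floor | Extra control days (mean) | Risk 10% | Risk 30% | Risk 50% |
|---|---|---|---|---|---|
| 14 | 69% | 1.8 | −1.2 | −2.8 | −3.5 |
| 18 | 43% | 1.05 | −0.5 | −1.4 | −1.8 |
| 21 | 26% | 0.6 | −0.3 | −0.7 | −0.9 |
| 25 | 12% | 0.3 | −0.1 | −0.3 | −0.4 |

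With 7.22 days in both arms the range is −0.06 to −2.5. With 12 days in both (an assumption beyond the cited figures) it is −0.3 to −4.5.

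**4. Effect on a true harm.** Let h = −ln(1 − base risk)/floor. A case that overruns by x days has risk 1 − (1 − base)·exp(−h·x). Take a 21-day floor, base risk 30%, and half of mucositis cases overrunning by 7 days.
- h = 0.3567/21 = 0.0170, so an overrunning case has risk 1 − 0.70 × exp(−0.119) = 0.378.
- Control: 0.30 + 0.50 × 0.5 × 0.078 = 0.320. Caphosol: 0.30 + 0.20 × 0.5 × 0.078 = 0.308. Artefact: −1.2 points.
- Repeating this with a Caphosol base risk of 35% or 40%, a true +5 is seen as +3.9 and a true +10 as +9.0.

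**5. Continuous reporting over many courses.** Same formula with an assumed 90-day period, 7 extra days at the end, and every mucositis case overrunning: 0.30 × (extended risk − base risk).
- Base 20%: 0.30 × (0.2138 − 0.20) = 0.4 points.
- Base 60%: 0.30 × (0.6275 − 0.60) = 0.8 points.

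**6. Sampling error.** The SE of a 10-point difference with 48 per arm is √[(0.05×0.95 + 0.15×0.85)/48] = 6.0 points for 5% v 15%, and √[(0.30×0.70 + 0.40×0.60)/48] = 9.7 points for 30% v 40%.

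**The case against.** A reader might infer that adverse events are followed only until mucositis resolves. The documents do not say that. In both arms there is a floor of 7 days after chemotherapy plus ANC recovery, and only mucositis that outlasts it extends the window.

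A reader might also infer that real harm is hidden, or that a true 5-point harm could vanish. That does not follow either. After the window, treatment-related events meeting expedited criteria are still reported on knowledge, unanticipated related problems are reportable to Day 60 or the start of a new treatment (Section 8.3), and deaths count to end of study (Section 8.2). What goes uncounted is mostly unrelated background events. An artefact of 0.8 to 5.0 points can be produced only by letting every mucositis case run 3 to 7 days past the floor in a single course. The 5.0 needs a 60% severe-event risk within 12 days as well.

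The strongest objection is that the plan can be read as one continuous period. Section 5.4 continues Caphosol with each eligible course, Section 5.6.1 defines completion as the end of all eligible cycles, and Section 5.5 collects data through planned therapy. On that reading the outcome-dependent tail falls mainly at the last course, plus any cycle delay. This stands, and it is why the lower range is given. It is not settled, because Section 5.5 also ties evaluations to each chemotherapy administration. The constant hazard may also overstate the tail, since the added days come after count recovery.

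None of this supplies a common window or an adjustment for time observed. Section 8.2 justifies its window by when treatment-related events are expected. That rationale suits attributed toxicity, not an all-cause comparison between arms.

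**Conclusion.** The concern holds in limited form, as a minor point. The end of adverse event observation depends partly on the efficacy outcome, and Section 10.1 compares incidence without allowing for it. If Caphosol works, it looks safer by about 0.1 to 3.5 points in a single course under the assumptions above, and by under 1 point over an assumed continuous 90 days. If it has no effect on mucositis, this tilt is absent.

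The bias is small beside the 10% boundary and a standard error of roughly 6 to 10 points. It could take up a material part of the 5% boundary when counts recover early and severe events are common. The ANC recovery days, event risks and chemotherapy length are not in the documents, and the cited durations come from adult transplant patients.

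The undefined reporting end for controls (Section 8.3) and the stop at removal from protocol therapy (Section 5.5) are separate gaps that the figures do not include. The second acts in the same direction, by shortening Caphosol-arm follow-up.

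**What to change.** In Sections 8.2, 8.3 and 10.1, for the between-arm comparison only:

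- Count severe adverse events over one fixed number of days from Day 1 of each eligible chemotherapy course. Make it the same in both arms and no longer than the shortest planned course interval, so that windows do not overlap.
- Count them whether or not mucositis has resolved or the study product has been stopped.
- Summarise per patient as any severe event in the first course, and report events per patient-day over all courses as support.
- Define the end of the reporting period for controls.
- Reconcile Section 10.1, which compares arms, with Section 10.3, which says toxicity can be estimated only in the treatment group.

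Leave the rules for stopping the rinse and for expedited reporting as they are. A common fixed window removes the artefact by construction; the patient-day rate does so only if the hazard is constant.

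The cost is some wording and a few more days of chart review for some patients. Events after the fixed day would be reported but not counted in the comparison.
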